13. DIRECT ACCESS TO SOURCE DATA/DOCUMENTS

Data collected during this study may be used to support the development, registration or marketing of ¹⁸F-DCFPyL. All data collected during the study will be controlled by Progenics or designee and Progenics will abide by all relevant data protection laws.

The investigator will grant monitor(s) and auditor(s) from Progenics or its designee and regulatory authority(ies) access to the subject's original medical records for verification of data entered into the eCRF and to audit the data collection process. The subject's confidentiality will be maintained and will not be made publicly available to the extent permitted by the applicable laws and regulations.

13.1. Study Monitoring

Before an investigational site can enter a patient into the study, a representative of Sponsor will visit the investigational study site to:

- Determine the adequacy of the facilities
- Discuss with the investigator(s) and other personnel their responsibilities with regard to protocol adherence, and the responsibilities of Progenics or its representatives. This will be documented in a Clinical Study Agreement between Progenics, or designee and the investigator.

During the study, a monitor from Progenics or designee will have regular contacts with the investigational site, for the following:

- Provide information and support to the investigator(s)
- Confirm that facilities remain acceptable
- Confirm that the investigational team is adhering to the protocol, that data are being accurately recorded in the case report forms, and that investigational product accountability checks are being performed
- Perform source data verification. This includes a comparison of the data in the case report forms with the patient's medical records at the hospital or practice, and other records relevant to the study. This will require direct access to all original records for each patient (e.g., clinic charts).
- Record and report any protocol deviations not previously sent to the Sponsor, or designee.
- Confirm AEs and SAEs have been properly documented on CRFs and confirm any SAEs have been forwarded to the Sponsor, or designee, and those SAEs that met criteria for reporting have been forwarded to the IRB.
- Confirm serious/unexpected/related SAE notification letter(s) from the Sponsor have been acknowledged and returned to the Sponsor.

The monitor will be available between visits if the investigator(s) or other staff needs information or advice.

13.2. Audits and Inspections

Authorized representatives of the Sponsor, a regulatory authority, an Independent Ethics Committee or an Institutional Review Board may visit the site to perform audits or inspections, including source data verification. The purpose of a Sponsor audit or inspection is to systematically and independently examine all study-related activities and documents to determine whether these activities were conducted, and data were recorded, analyzed, and accurately reported according to the protocol, Good Clinical Practice guidelines of the International Conference on Harmonization, and any applicable regulatory requirements.

The investigator should contact Progenics immediately if contacted by a regulatory agency about an inspection, and will provide Progenics with the results of any such audits and with copies of any regulatory documents related to such audits.

14. ETHICS

This clinical trial will be conducted in accordance with the ethical principles that have their origin in the Declaration of Helsinki and that are consistent with GCP and applicable regulatory requirement(s). The rights, safety, and well-being of the trial subjects are the most important considerations and should prevail over interests of science and society.

14.1. Good Clinical Practice (GCP), Laws and Regulations

The investigator must ensure that he/she and all authorized personnel for the study are familiar with the principles of Good Clinical Practice (GCP) and that the study is conducted in full conformity with the current revision of the Declaration of Helsinki, ICH Guidelines and applicable local laws and regulations, with the understanding that local laws and regulations take precedence over respective sections in the Declaration of Helsinki and/or the ICH Guidelines.

14.2. Institutional Review Board (IRB) or Independent Ethics Committee (IEC) Approval

The final study protocol, including the final version of the Informed Consent Form, must be approved or given a favorable opinion in writing by an IRB or IEC as appropriate. The investigator must submit documented approval to the Sponsor before he or she can enroll any patient/subject into the study.

The Principal Investigator is responsible for informing the IRB or IEC of any amendment to the protocol in accordance with local requirements. In addition, the IRB or IEC must approve all advertising used to recruit patients for the study. The protocol must be re-approved by the IRB or IEC upon receipt of amendments and annually, as local regulations require.

The Principal Investigator is also responsible for providing the IRB with reports of any reportable serious adverse drug reactions from any other study conducted with the investigational product. The Sponsor, or designee, will provide this information to the Principal Investigator.

Progress reports and notifications of serious adverse drug reactions will be provided to the IRB or IEC according to local regulations and guidelines.

14.3. Written Informed Consent

The Principal Investigator(s) at each center will ensure that the patient is given full and adequate oral and written information about the nature, purpose, possible risk and benefit of the study. Patients must also be notified that they are free to discontinue from the study at any time. The patient should be given the opportunity to ask questions and allowed time to consider the information provided.

The patient's signed and dated informed consent must be obtained before conducting any study procedures.

The Principal Investigator(s) must maintain the original, signed Informed Consent Form. A copy of the signed Informed Consent Form must be given to the patient.

14.4. Subject Confidentiality

The Investigator must ensure that the subject's privacy is maintained. A subject should only be identified by their date of birth and subject number on the case report forms or other documents submitted to the Sponsor. Documents that are not submitted to the Sponsor (e.g., signed informed consent form) should be kept in a strictly confidential section of the study file by the Investigator.

Written authorization is to be obtained from each subject prior to enrollment into the study in accordance with the applicable privacy requirements [e.g., the Health Insurance Portability and Accountability Act of 1996 Standards for Privacy of Individually Identifiable Health Information ("HIPAA") and any other state and country privacy requirements].

14.5. Financial Disclosure

All investigators must provide financial disclosure information in accordance with the US Code of Federal Regulations Title 21 CFR 54.2 through 54.6.

15. DATA HANDLING AND RECORDKEEPING

15.1. Case Report Forms and Study Records

Progenics or designee will provide an electronic case report form (eCRF) and eCRF Completion Guidelines for the entry of study data. eCRFs must be completed for each subject. All study data must be reported accurately on eCRFs from original source data. Source documents are original documents, data and records (e.g., hospital records, office charts, laboratory notes, memoranda, evaluation checklists, pharmacy dispensing records, recorded data from automated instruments, magnetic media, diagnostic images, subject files). The investigator will make available the source documents for inspection. This information will be considered as confidential.

The use of eCRFs will encompass electronic data entry, query management and investigator approval. Systems used for electronic data capture will be compliant with FDA regulations 21 CFR Part 11 and within the constraints of the applicable local regulatory agency guidelines.

The Investigator or designee will review, sign and date the completed eCRF sections. This signature will indicate a thorough inspection of the data in the eCRF and will certify its content.

15.2. Inspection of Records

The Sponsor, or designee, will be allowed to conduct site visits to the investigation facilities for the purpose of monitoring any aspect of the study. The Investigator agrees to allow the monitor to inspect the drug storage area, study drug stocks, drug accountability records, subject charts and study source documents, and other records relative to study conduct. See Section 13.2.

15.3. Retention of Records

The Principal Investigator must maintain all documentation relating to the study for a period of 2 years after the last marketing application approval, or if not approved 2 years following the

discontinuance of the test article for investigation. If it becomes necessary for the Sponsor or the Regulatory Authority to review any documentation relating to the study, the Investigator must permit access to such records. No study document should be destroyed without prior written agreement between Sponsor and the investigator.

16. PUBLICATION AND DISCLOSURE POLICY

All unpublished documentation [including the protocol, eCRF and Investigator Brochure (IB)] given to the investigator is strictly confidential. All recipients must agree not to disclose the information herein contained to any person without the prior written authorization of Progenics. The submission of these documents to the IRB is expressly permitted.

The investigator agrees that Progenics maintains the right to use the results of this study in their original form and/or in a global report for submission to governmental and regulatory authorities of any country.

The results of the study may be presented during scientific symposia or published in a scientific journal only after review by Progenics in accordance with the guidelines set forth in the applicable publication or financial agreement.

Progenics

# 1. LIST OF ABBREVIATIONS

**Table 1: List of Abbreviations** 

Abbreviation	Term
 F	fluorine 18
ADT	androgen deprivation therapy
AE	adverse event
ATC	anatomical therapeutic classification
AUC	area under the curve
BN	bone
BP	blood pressure
CI	confidence interval
C max	maximum observed concentration
CL	clearance
cm	centimeter
СРМ	counts per minute
CT	computed tomography
ECG	electrocardiogram
eCRF	electronic case report form
eGFR	estimated Glomerular filtration rate
ePLND	Extended lymph node dissection in prostate cancer
FN	false negative
FP	false positive
HR	heart rate
ICH	International Council for Harmonisation of Technical Requirements for Pharmaceuticals for Human Use
I(p)	total positive imaging
I(n)	total negative imaging
Kg/m 	kilograms per metered squared
LLN	lower limit of normal
LN	lymph node
MBq	Megabecquerel
mCi	millicurie
MDRD	Modification of diet in renal disease study

**Table 1: List of Abbreviations** 

Abbreviation	Term	
MedDRA	Medical Dictionary for Regulatory Activities	
mL	milliliter	
MRI	magnetic resonance imaging	
MRT	mean residence time	
NC	North Carolina	
ng/mL	nanogram/milliliter	
NPV	negative predictive value	
PET/CT	positron emission tomography/computed tomography	
PK	pharmacokinetics	
PPV	positive predictive value	
PSA	prostate specific antigen	
PSMA	Prostate specific membrane antigen	
PT	preferred term	
R(n)	total negative histopathology	
R(p)	total positive histopathology	
RP	radical prostatectomy	
RR	respiratory rate	
SAE	serious adverse event	
SAP	statistical analysis plan	
SCr	serum creatinine	
SD	standard deviation	
SOC	system organ class	
ST	Soft tissue	
SUV max	maximum standardized uptake value	
SUV mean	Mean standardized update value	
$SUV_{peak}$	peak standardized uptake value	
$SUV_r$	ratio to reference tissue standardized uptake value	
TEAE	treatment-emergent adverse event	
T 1/2	half life	
T 1/2alpha	alpha phase distributive half life	
T 1/2beta	beta phase elimination help life	

**Table 1: List of Abbreviations** 

Abbreviation	Term
T 1/2elim	elimination half life
$T_{\text{max}}$	time to maximum concentration
TN	true negative
TOA	time of administration
TP	true positive
ULN	Upper limit of normal
USA	United States of America
$V_{ss}$	steady state volume of distribution
WHODD	World Health Organization Drug Dictionary

#### 2. INTRODUCTION

The statistical analysis plan (SAP) is based on:

- Protocol amendment 2 dated November 6, 2017,
- ICH guidelines E6 and E9.

The purpose of this document is to provide details about study populations, how variables will be derived, how missing data will be handled as well as details about statistical methods to be used to analyze the safety and efficacy data from Study PyL-2301.

The list of tables, listings and their shells are guidelines which may be refined to facilitate programming. Such changes will not be documented in an amendment to this document. However, any changes to populations, endpoints or analysis methods will be documented in a SAP amendment and will be noted in the clinical study report, as relevant.

#### 3. STUDY OBJECTIVES AND ENDPOINTS

## 3.1. Study Objectives

#### 3.1.1. Primary Objective

The primary objective of the study is to assess the diagnostic performance of F-DCFPyL PET/CT imaging to determine the presence or absence of metastatic disease in pre-prostatectomy subjects with high risk prostate cancer (cohort A).

#### 3.1.2. Secondary Objectives

- 1. To evaluate the safety and tolerability of F-DCFPyL
- 2. To assess the diagnostic performance of F-DCFPyL PET/CT imaging to determine the presence or absence of prostate cancer within sites of metastasis or local recurrence (cohort B).
- 3. To determine detection rates of F-DCFPyL PET/CT and conventional imaging among lesion locations (e.g., bone, lymph nodes, soft tissue, prostate gland)
- 4. To determine positive and negative predictive value (PPV and NPV) of F-DCFPyL PET/CT imaging
- 5. To determine the pharmacokinetics, bio-distribution and excretion of F-DCFPyL

## 3.1.3. Exploratory Objectives

- 1. To assess F-DCFPyL uptake among lesion locations (e.g., bone, lymph nodes, soft tissue, prostate gland)
- 2. To assess the relationship between F-DCFPyL uptake in prostatic and extra-prostatic lesions with baseline PSA and testosterone levels and Gleason Score at time of radical prostatectomy
- 3. To assess the diagnostic performance of F-DCFPyL PET/CT imaging to detect prostate cancer within the prostate gland (Cohort A)
- 4. To assess the impact of F-DCFPyL PET/CT imaging on clinical management plan
- 5. To determine PPV of F-DCFPyL PET/CT imaging for lesions detected by PET that are outside the planned surgical template or biopsy site

## 3.2. Efficacy Endpoints

#### 3.2.1. Primary Efficacy Endpoints

- 1. Specificity of F-DCFPyL PET/CT imaging to determine the absence of metastatic prostate cancer within the pelvic lymph nodes relative to histopathology in Cohort A
- 2. Sensitivity of F-DCFPyL PET/CT imaging to determine the presence of metastatic prostate cancer within the pelvic lymph nodes relative to histopathology in Cohort A

#### 3.2.2 Secondary Efficacy Endpoints

- 1. Sensitivity of F-DCFPyL PET/CT imaging to detect prostate cancer within sites of metastasis or local recurrence relative to histopathology in Cohorts B
- 2. Comparison of detection rates for lesion counts overall and by location (i.e., bone, lymph nodes, soft tissue, prostate gland) between F-DCFPyL PET/CT and conventional imaging in Cohorts A and B combined
- 3. PPV of F-DCFPyL PET/CT imaging to predict prostate cancer within the prostate gland and lymph nodes in Cohort A
- 4. NPV of F-DCFPyL PET/CT imaging to predict the absence of prostate cancer within the prostate gland and lymph nodes in Cohort A
- 5. PPV of F-DCFPyL PET/CT imaging to predict prostate cancer within sites of local recurrence and other metastatic lesions in Cohort B
- 6. Pharmacokinetic parameters derived from blood samples [e.g., Cmax, area under the curve (AUC), total clearance (CL), steady-state volume of distribution (Vss), and mean residence time (MRT)] (subset of Cohorts A and B combined)

#### 3.2.3 Exploratory Efficacy Endpoints

- 1. F-DCFPyL uptake in different lesion locations as defined by SUVpeak, SUVmax, and SUVr results derived from central readers for cohorts A and B combined and compared between histology outcomes
- 2. To assess the relationship between SUVpeak, SUVmax, volume, and SUVr and Gleason Score at time of radical prostatectomy, baseline PSA, and testosterone levels for both cohorts
- 3. Sensitivity of F-DCFPyL PET/CT imaging within the prostate gland relative to histopathology in Cohort A
- 4. Specificity of F-DCFPyL PET/CT imaging within the prostate gland relative to histopathology in Cohort A
- 5. Changes to clinical management based on a review of clinical and radiographic subject data before and after F-DCFPyL PET/CT imaging by a central panel of disease experts using a structured questionnaire (Cohort A only)
- 6. PPV of F-DCFPyL PET/CT imaging in subjects with corresponding histopathology for subjects who had a change in the planned protocol procedure (Both Cohorts combined)

## 3.3. Safety Endpoints

- 1. Treatment-emergent adverse events (TEAEs) and SAEs
- 2. Change from baseline in clinical laboratory parameters
- 3. Change from baseline in ECGs
- 4. Change from baseline in vital signs
- 5. Concomitant medication use

#### 4. STUDY DESIGN

## 4.1. Summary of Study Design

This is an open-label, non-randomized, Phase 2/3, multi-center study designed to evaluate the safety and diagnostic performance of F-DCFPyL PET/CT imaging to determine the presence or absence of metastatic prostate cancer in subjects with high risk prostate cancer who were planned for radical prostatectomy with pelvic lymph node dissection (cohort A), and subjects with radiologic evidence of local recurrence or new or progressive metastatic disease (cohort B) who were biopsied if a positive lesion was found on the F-DCFPyL PET/CT scan. The physician has the option to change the planned protocol specified procedure (i.e., RP ePLND for Cohort A subjects and Biopsy for Cohort B subjects) for the subjects based on the F-DCFPyL PET/CT scan. The details of these changes will be collected on the CRF, and these subjects obviating the planned procedure will not be included in any of the primary or secondary endpoints.

Eligible subjects will be enrolled in a non-randomized, sequential manner, with competitive enrollment between study sites. Ten (10) study sites will be used in the U.S. and Canada.

[figure not shown]
Diagnostic performance characteristics of F-DCFPyL PET/CT imaging will be evaluated using histopathology as the truth standard. Three independent readers from a central imaging core lab will be given access to F-DCFPyL PET/CT imaging, conventional imaging, and biopsy-guided imaging. The central readers will be blinded to all other clinical information (i.e. pathology data) and radiology assessments. Likewise, local pathologists who generate the histopathology results for the primary endpoint are blinded to all imaging results.

A change in clinical management questionnaire will be filled out by an independent urologist who is not otherwise a participant of the study. To maintain the blind for imaging, a statistician who is independent from the PyL study team will generate subject listings. A combination of imaging and clinical data will then be posted to a share point site where the independent urologist will review these data and fill out the questionnaire based on the results he sees prior to PyL imaging and then again after PyL imaging. To keep things simple, only imaging data from reviewer 1 will be presented for this assessment to be performed.

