7. SELECTION AND WITHDRAWAL OF SUBJECTS

7.1. Subject Inclusion Criteria

Subjects must meet all of the following inclusion criteria:

All Cohorts:

- 1. Adults ≥ 18 years of age.
- 2. Subjects provide signed informed consent and confirm that they are able and willing to comply with all protocol requirements.
- 3. Histologically confirmed adenocarcinoma of the prostate.

Cohort A Only:

- 4. At least high risk prostate cancer defined by NCCN Guidelines Version 3.2016 (clinical stage \geq T3a or PSA >20 ng/mL or Gleason score \geq 8).⁴⁷
- 5. Scheduled or will be scheduled to undergo radical prostatectomy with PLND.

Cohort B Only:

- 6. Radiologic evidence of local recurrence or new or progressive metastatic disease demonstrated on anatomical imaging (CT, MRI, or ultrasound), whole-body bone scan (^{99m}Tc-MDP or Na¹⁸F) within 4 weeks of Day 1.
- 7. If prior treatment with radiation or ablative therapy, evidence of recurrence outside the confines of prior treated site(s).
- 8. Scheduled or will be scheduled for percutaneous biopsy of at least one amenable lesion.

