8.4. Randomization and Blinding

This is an open-label, non-randomized study. Three independent readers from a central imaging core lab will be given access to ¹⁸F-DCFPyL PET/CT imaging, conventional imaging, and biopsy-guided imaging. The central readers will be blinded to all other clinical information and radiology assessments. Likewise, the Investigator is responsible for ensuring that local pathologists who generate the histopathology results for the primary endpoint remain blinded to all imaging results.

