10.1.4. Biopsy Guided Imaging (cohort B only)

In Cohort B, imaging used to guide biopsy (i.e., CT/MRI) will be collected and reviewed centrally to confirm the biopsy location in the area of interest. The instruction for capturing biopsy images and directions for submitting the images to the independent central imaging core lab will be found in the Image Guided Biopsy Manual.

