10.4. Interventional Radiology

Up to two lesions (one bone and one soft-tissue lesion, wherever feasible) may be biopsied in cohort B, within 28 days following ¹⁸F-DCFPyL imaging. If more than one lesion is obtained, the interventional radiologist will identify the specimen to be evaluated for diagnostic assessment and statistical analysis. The lesions most preferred for biopsy will be those that are suspicious on all or most imaging modalities and are in the investigators judgement safe for biopsy. The final biopsy site will be decided in consultation with the Interventional Radiology service for feasibility. Details regarding the collection of imaging used to guide biopsy (e.g., X-ray, CT, MRI) and transmittal to the central imaging lab can be found in the Image Guided Biopsy Manual. Images will be reviewed centrally to confirm uptake of ¹⁸F-DCFPyL in the area of interest.

Should a subject receive alternate or additional procedure(s) for prostate cancer after dosing, the procedure and corresponding histopathology data will be recorded in the eCRF.

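### SAP 4.1 makes Cohort B biopsy conditional on a positive study PET, against the rest of the plan; if it was followed, Cohort B sensitivity is biased upward

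*SAP*

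**What the plan says.** SAP 4.1 summarises Cohort B as subjects with radiologic recurrence or progression "who were biopsied if a positive lesion was found on the" study scan. It then lets the physician change the planned procedure in the light of that scan, in either cohort, and adds that "these subjects obviating the planned procedure will not be included in any of the primary or secondary endpoints". SAP 4.2 expects few such subjects.

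Elsewhere biopsy does not depend on PET. Protocol 7.1, criterion 8, requires at entry: "Scheduled or will be scheduled for percutaneous biopsy of at least one amenable lesion". SAP 4.2 sends every subject from imaging to biopsy or surgery. The evaluable sets (Protocol 12.2.3, SAP 5.4.3) accept either PET result, and SAP 5.5.7.2 scores a biopsied lesion without uptake as PET negative.

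On the choice of lesion, Protocol 10.4 places biopsy after imaging and states: "The lesions most preferred for biopsy will be those that are suspicious on all or most imaging modalities". It also states: "If more than one lesion is obtained, the interventional radiologist will identify the specimen to be evaluated for diagnostic assessment and statistical analysis".

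Protocol 12.5.2.2 gives Cohort B sensitivity a success rule: the lower 95% limit must exceed 0.50 for at least two of three central readers. SAP 7.7.2 keeps the 0.5 null. Protocol 12.1 plans about 115 dosed subjects without a power calculation.

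**The concern.** Sensitivity is TP/R(p), and R(p) counts only cancers proved by biopsy. If a positive PET leads to biopsy and a negative one does not, missed cancers never enter R(p). False negatives are lost, and the estimate rises whatever the tracer's true performance. A tracer with true sensitivity 0.50 could then be declared better than 0.50.

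The condition in SAP 4.1 would do this directly. The physician's option to change the procedure would do it in part, because those subjects leave the secondary endpoints. They are analysed only for PPV (SAP 7.8), which cannot reveal missed disease. A reader of the Cohort B result could not tell from the plan which biopsy rule produced it.

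**Working it through.** **1. The passages side by side**

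| Place | Biopsy conditional on a positive PET? |
|---|---|
| SAP 4.1 | Yes |
| Protocol 7.1, criterion 8 | No, planned at entry |
| SAP 4.2 | No |
| Protocol 12.2.3, SAP 5.4.3 | No, either PET result is evaluable |
| SAP 5.5.7.2 | No, PET-negative biopsied lesions are scored |
| SAP 10 (changes from protocol) | Not listed |

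SAP 4.1 cannot be in force together with the others.

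**2. The plan's own figures.** The Cohort A size reproduces: 47.09/0.20 = 235.5, so 236 evaluable, and 236/0.9 = 262.2, stated as about 262. For Cohort B the plan gives only the 115 dosed (262 + 115 = 377). It gives no expected sensitivity and no biopsy rate by PET result, so everything below is illustration.

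**3. Direction of bias.** Let s be true sensitivity and f the chance that a PET-negative cancer lesion is biopsied, relative to a PET-positive one. If the read that steers biopsy equals the central read,

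observed sensitivity o = s / [s + (1 − s)f],

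which exceeds s for any f < 1 (0 < s < 1). At s = 0.50:
- f = 0.75: 0.50/0.875 = 0.57
- f = 0.5: 0.50/0.75 = 0.67
- f = 1: 0.50, no bias

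**4. False pass per reader.** Let N be the number of diseased biopsy candidates. N is assumed to be 50 to 103; 103 is about 90% of 115, borrowing the 10% non-evaluable rate from Cohort A. The number biopsied is n ~ Bin(N, s + (1 − s)f), and TP given n ~ Bin(n, o). A pass is a lower 95% normal-approximation limit above 0.50. The SAP's Agresti-Coull fallback, applied when a cell is 5 or fewer, changes nothing. Exact results at s = 0.50:

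| f | N = 50 | N = 80 | N = 103 |
|---|---|---|---|
| 1 | 0.0325 | 0.0283 | 0.0241 |
| 0.75 | 0.1747 | 0.2404 | 0.2888 |
| 0.5 | 0.5743 | 0.7658 | 0.8562 |

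**5. When the steering read is not the central read.** The site decides on biopsy, but blinded central readers are scored. Let any two reads of a cancer lesion agree with probability q. At s = 0.50,

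o = [q + f(1 − q)] / (1 + f).

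With q = 0.8, f = 0.75 gives 0.95/1.75 = 0.54 and f = 0.5 gives 0.90/1.5 = 0.60. Chance of passing the two-of-three rule at q = 0.8 (40,000 simulations per cell):

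| f | N = 50 | N = 80 | N = 103 |
|---|---|---|---|
| 1 | 0.018 | 0.015 | 0.013 |
| 0.75 | 0.070 | 0.091 | 0.108 |
| 0.5 | 0.225 | 0.350 | 0.429 |

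If the steering read is independent of the central reads, q = 0.5 here and o = 0.5(1 + f)/(1 + f) = 0.50 for every f. There is then no bias.

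**6. Can it be undone afterwards?** Inverting step 3 gives s = of/(of + 1 − o). At o = 1.00 this returns 1.00 for every f > 0, so it says nothing in the extreme case. With q = 0.8 and f = 0.5 it turns o = 0.60 into 0.30/0.70 = 0.43, below the true 0.50. It over-corrects when reads disagree and can serve only as a bound.

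**The case against.** **The clause is one line in an SAP design summary.** The protocol directs the sites, and neither criterion 8 nor section 10.4 conditions biopsy on PET. The operative SAP definitions provide for PET-negative biopsies. This stands: a drafting slip is quite possible, and a reader should not infer that biopsy was in fact conditional on PET.

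**The central-review passages can be read together.** Protocol 10.4 says "Images will be reviewed centrally to confirm uptake of" the tracer at the site, while 10.1.4 says biopsy images "will be collected and reviewed centrally to confirm the biopsy location in the area of interest". A reader might infer that only lesions with uptake were accepted. The text does not support that, because SAP 5.5.7.2 records uptake at the biopsied lesion as yes or no, and checking uptake fits that scoring step.

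**The target is tied to conventional imaging.** Criterion 6 requires recurrence or progression on conventional imaging, and SAP 5.4.3 requires a biopsy guided by it. The lesion preference in 10.4 does not say that the study PET must be among the suspicious modalities. This lowers the risk but does not exclude PET influence. Biopsy follows PET, and the interventional radiologist picks the analysed specimen. Protocol 8.4 states blinding for the central readers and requires that "local pathologists who generate the histopathology results for the primary endpoint remain blinded to all imaging results". It is silent on whoever chooses the lesion.

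**Some planned outputs bear on this.** Disposition counts the changed-procedure set (SAP 6.1). Tables 14.2.3-11 to 14.2.3-13 summarise imaging, histology and procedures. Listing 16.2.3-1 gives exclusions, and a nearly empty false-negative cell would itself be a signal. So it would be wrong to infer that nothing planned could reveal the problem. What is missing is narrower: no listed output is titled as biopsy status by PET result in Cohort B, and no analysis addresses selective verification.

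**The endpoint is secondary.** It has no power calculation and is analysed whatever the primary result. This limits the consequence, but the protocol still attaches a reject rule to it.

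**Conclusion.** The contradiction between SAP 4.1 and the rest of the plan is real and should be resolved. Whether Cohort B sensitivity is biased depends on which rule was followed, and the documents available here do not show that. If biopsy depended on PET, the direction is upward unless the steering read is unrelated to the central reads.

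The size cannot be determined. Under the assumptions above, with true sensitivity 0.50 and f = 0.75 or 0.5:
- Steering read equal to the central read: apparent sensitivity 0.57 or 0.67, false pass per reader 17–29% or 57–86%.
- 80% agreement between reads: apparent sensitivity 0.54 or 0.60, two-of-three false pass about 7–11% or 23–43%.
- f = 1: no bias.

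A reader might also infer that SAP 4.1 forces 100% sensitivity. It need not. Site and central reads can differ, and a positive lesion elsewhere could lead to biopsy of a PET-negative one. The biopsy condition concerns Cohort B only, so the Cohort A primary conclusion is unaffected. This is a change that should be made, held with medium confidence.

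**What to change.** 1. Reconcile SAP 4.1 with Protocol 7.1 and 12.2.3 and with SAP 4.2, 5.4.3 and 5.5.7.2 on whether Cohort B biopsy depends on the study PET. This point takes no position on which biopsy rule applies.
2. In SAP 7.7.2, add one Cohort B table of subjects biopsied and not biopsied, by PET result and reader, with reasons. A subject-level table cannot show which lesion was chosen, so also state whether the analysed lesion was selected with knowledge of the PET, if that was recorded.
3. If the reconciliation or the table shows that biopsy depended on PET, report sensitivity as conditional on biopsied lesions and without the 0.50 success claim. Show any f-based correction only as a bound. Otherwise the comparison with 0.50 stays.

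The cost is some wording and one table, largely from data already planned for collection, with no new subjects or procedures. The downside is a little more analysis and one secondary claim that may need qualifying.
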